## **Funder**

There is no funder for the study as it is an MSc project

This protocol describes 'Virtual Reality as a Distraction technique for management of acute pain at outpatient hysteroscopy' and provides information about the procedures for entering participants. Every care was taken in its drafting, but corrections or amendments may be necessary. These will be circulated to investigators in the study. Problems relating to this study should be referred, in the first instance, to the Chief Investigator.

This study will adhere to the principles outlined in the NHS Research Governance Framework for Health and Social Care (2nd edition). It will be conducted in compliance with the protocol, the Data Protection Act and other regulatory requirements as appropriate.

## **GLOSSARY OF ABBREVIATIONS**

OPH	Outpatient Hysteroscopy
VR	Virtual Reality

## **KEYWORDS**

Distraction techniques

Acute pain

Outpatient Hysteroscopy

## STUDY SUMMARY

TITLE	Virtual Reality as a Distraction technique for management of acute pain at Outpatient Hysteroscopy
DESIGN	Randomised Control Trial with Mixed methods – Qualitative and quantitative
AIMS	To study the role of distraction techniques for management of acute pain in Outpatient Hysteroscopy and to assess feasibility of using Virtual Reality for managing pain.
OUTCOME	Primary objective:
MEASURES:	

• Feasibility of using virtual reality as a distraction technique in management of acute pain in patients undergoing Outpatient Hysteroscopy.

	Secondary objectives:
	

• Understanding the acceptability and effectiveness of VR interventions within the procedural groups and how these might vary as a function of different patient demographics.

• Understanding the factors that might influence the willingness of patients to participate in a future formal trial of the technology.

• Understanding how best to implement the technology and designing of the contents of the VR intervention.

• Understanding the effective mechanisms for the analgesic effect of VR and explore how this could be tailored to individual patients.

POPULATION	Patients attending the Outpatient Hysteroscopy clinics
ELIGIBILITY	Patients undergoing Outpatient Hysteroscopy

DURATION	6 months
-----------------	----------

## **1. INTRODUCTION**

### **1.1 BACKGROUND**

Performing procedures for investigation and treatment of gynaecological conditions in the office setting is becoming commonplace. Outpatient gynaecological procedures can reduce risks of general anaesthetic, decrease health care costs and make the procedure more convenient for the patient and provider. However, ensuring adequate pain relief and allaying anxiety during the procedure can prove to be challenging. Appropriate patient selection, counselling and adequate pain management during the procedure can improve patient experience and reduce the number of failed procedures.

Common office gynaecological procedures include outpatient hysteroscopy, colposcopy and large loop excision of transformation zone, manual vacuum aspiration for treatment of miscarriages, intrauterine contraceptive device insertion, hysteroscopic sterilisation and endometrial biopsy.

Pain in gynaecological procedures can originate from the cervix and uterus. The uterine fundus is innervated by sympathetic fibres from T10 to L2, which enter through the uterosacral ligaments via the inferior hypogastric plexus, and by nerves from the ovarian plexuses at the cornua. Parasympathetic fibres from S2 to S4 travel through the broad ligament to enter the cervix at the 3 o clock and 9 o clock positions to provide innervation to the upper vagina, cervix and the lower uterine segment. The pudendal nerve (S 2,3, 4) supplies the lower vagina and vulva.

Physical, psychological and social factors influence the intensity of pain experienced. Counselling the patients pre procedurally helps to better manage expectations and pain.

Outpatient hysteroscopy is usually performed for patients having abnormal uterine bleeding and subfertility. Pain levels during this procedure can be influenced by the

diameter of the hysteroscope. Mini hysteroscopes with an outer diameter of 3.5 mm have been associated with lower pain scores. (Paulo et al., 2015) Additional procedures performed (like polypectomy or Coil insertions) could increase the duration of the procedure and the pain experienced during the procedure. Pain scores in the vaginoscopic approach have been noted to be 3.8 when compared to 5.3 in the traditional group, which uses a speculum and tenaculum. (Sagiv et al., 2006)

Pain in hysteroscopy is significantly related to the presence of cervical synechiae, to the duration of the procedure, and to the use of normal saline; conversely, parity seems to have a protective role.(Mazzon et al., 2014)

Previous vaginal deliveries, experience of the operator and quicker operative time are known to be associated with successful outcomes of the outpatient procedures. However, nulliparity, postmenopausal status, anxiety and anticipated pain and a history of dysmenorrhoea are known to be associated with higher perception of pain and reduced success rates. (Ireland and Allen, 2016, de Carvalho Schettini et al., 2007)

The type of pain relief offered can include various levels of sedation, local anaesthetic, analgesics and verbal support techniques through distraction by conversation, gentle language, music, guided imagery and positive suggestion. A Cochrane Review showed no consistent good quality evidence of a significant difference in safety or effectiveness between different types of pain relief compared with each other or with placebo/ no treatment. (Ahmad et al., 2010) There is no consensus on the choice of analgesia for outpatient hysteroscopy and rescue analgesia in the form of intracervical blocks is often used. (O'Flynn et al., 2011)

In the UK, most units offer analgesics either as NSAIDs, acetaminophen or oral opioids. NSAIDS such as ibuprofen decrease uterine activity and pain by inhibiting cyclooxygenase and thereby reduce circulating prostaglandins. They reduce pain levels especially postoperatively. Acetaminophen also inhibits the enzyme cyclooxygenase, but its action is in the central nervous system rather in the periphery. Hence is inferior to NSAIDS but is offered to women who cannot tolerate NSAIDS. Oral opioids act by interacting with endogenous opioid mu receptors. (Ireland and Allen, 2016)

The only pharmacological method that has demonstrated its effectiveness in reducing pain during and 30 minutes after hysteroscopy in several meta-analysis and reviews is paracervical block. (del Valle et al., 2016) However, it fails to anaesthetise the uterus for intrauterine procedures and a previous Cochrane review was unable to confirm this. (Tangsiriwatthana et al., 2009) The administration of the local anaesthetic itself may be uncomfortable, have side effects due to toxicity, may cancel the beneficial effect of performing a vaginoscopic hysteroscopy and does not anaesthetise the uterus. Addition of soda bicarbonate as a buffering agent to the local anaesthetic and using dental syringes with a 27-gauge needle has been seen to decrease the pain during the injection. Topical local anaesthetics on the cervix in the form of gel or sprays have not been shown to be effective.

Women undergoing outpatient hysteroscopy experience significant levels of preoperative anxiety which is higher than patients attending the gynaecology clinic and comparable to those experienced before major surgery under general anaesthesia. (Gambadauro et al., 2015, Gupta et al., 2004)

Anxiolytics help reduce anxiety, however they do not have a direct analgesic effect. Units often employ a trained person to engage with the patient to provide emotional support during the procedure.

### **Distraction Techniques**

Type of distraction techniques range from active distraction techniques to passive techniques. Active distraction included interactive toys, virtual reality, guided imagery and relaxation and controlled breathing. Passive distraction techniques included auditory distraction in the form of music and audio-visual distraction through watching television. Intraoperative pain and anxiety rating have been noted to be lower by use of simple intraoperative distraction techniques e.g. interacting with nurses, watching DVDs or using stress balls. (Hudson et al., 2015)

There has been limited research done on the role of distraction techniques in pain management in outpatient gynaecological procedures. Music has been used as a complementary method to control anxiety and reduce perception of pain by relaxing the patient and causing less discomfort during outpatient hysteroscopy. (Angioli et

al., 2014). However, a RCT showed no positive effect of music on patients' level of pain, anxiety or satisfaction of patient or doctor for office hysteroscopy and colposcopy.(Mak et al., 2017). Watching the procedure on the screen at office hysteroscopy has not been shown to reduce pain scores.(Ogden et al., 2009)

Women with high level of preprocedural state- trait anxiety are more likely to perceive higher levels of pain and discomfort during colposcopy. (Baser et al., 2013) Simple passive visual distraction during colposcopic examination was associated with a reduction in pain scores, however anxiety levels were unchanged. (Carwile et al., 2014) A Cochrane review in 2007 concluded that anxiety appears to be reduced by playing music during colposcopy. Although information leaflets did not reduce anxiety levels, they did increase knowledge levels and helped with consenting for the procedure. (Galaal et al., 2007)

Virtual reality is a relatively new intervention, which has been studied as a non-pharmacological method for pain relief. (Loreto-Quijada et al., 2013, Loreto-Quijada et al., 2014). VR as a form of managing pain has been studied in paediatrics, dentistry, burns treatment, treatment of chronic pain. (Hoffman et al., 2000) It has not been studied in the management of pain of gynaecological procedures, which are increasingly being performed as office procedures.

It acts as a method of distraction for pain relief by changing the activity of the body's pain modulation system. This multisensory technology gives an immersive and engaging experience and serves as a distraction technique. Head tracking systems, visually stimulating scenery and audio and tactile feedback enable integration of many sensory experiences. Different psychological factors influence the effectiveness of the analgesic effect of VR. While sense of presence influence the effectiveness of VR as a distraction tool, anxiety as well as positive emotions directly affects the experience of pain. (Triberti et al., 2014)

VR distraction has been associated with significant increases in pain threshold and pain tolerance and significant decreases in pain intensity, time spent thinking about pain, and self-reported anxiety, relative to baseline. Repeated exposure did not appear to affect the benefits of VR. (Rutter et al., 2009). Simultaneous exposure to VR and supplementary sound increases pain tolerance. (Johnson and Coxon, 2016)

Pain management in ambulatory procedures should be multimodal and should include both pharmacological and non-pharmacological interventions. Giving the patient a range of options will increase the number of successful procedures in the outpatient setting and improve patient experience.

## **1.2 RATIONALE FOR CURRENT STUDY**

To study the role of distraction techniques for management of acute pain in ambulatory gynaecology procedures and to assess feasibility of using Virtual Reality for managing pain.

## **2. STUDY OBJECTIVES**

Primary objective:

- Feasibility of using virtual reality as a distraction technique in management of acute pain in patients undergoing Outpatient Hysteroscopy.

Secondary objectives:

- Understanding the acceptability and effectiveness of VR interventions within the procedural groups and how these might vary as a function of different patient demographics.
- Understanding the factors that might influence the willingness of patients to participate in a future formal trial of the technology.
- Understanding how best to implement the technology and designing of the contents of the VR intervention.
- Understanding the effective mechanisms for the analgesic effect of VR and explore how this could be tailored to individual patients.

## **3. STUDY DESIGN**

The study is a randomised control trial involving mixed methods of qualitative and quantitative analysis. Participants will be recruited for the study at the Gynaecology Department at Whipps Cross University Hospital, Barts Health NHS Trust from June

2018 to October 2018. The patients will be identified from the gynaecology clinic by the clinicians who schedule them for Outpatient Hysteroscopy procedure. The study will include 40 patients attending the outpatient hysteroscopy clinic and randomised to either a VR intervention group or standard procedure by computer-generated randomisation.

They will be given a study information sheet, an invitation to participate with a reply slip to indicate whether they would like to participate in the study. Patients will be given standard pre procedural information about the procedure as per standard practice. Written informed consent will be obtained from participants and the interview outputs will be anonymised.

All patients will fill in a questionnaire before and after the procedure. Patients who have been randomised to the VR arm will have a semi-structured interview regarding their experience with VR.

The staff in the clinic will include a clinician performing the procedure and a staff nurse supporting the clinic. They will be given a study information sheet regarding the study and a written informed consent for a questionnaire will be obtained from them if they agree to participate. The clinician performing the procedure will fill in a questionnaire per patient regarding the ease of the procedure and perceived pain levels of the patient. The Clinician performing the procedure and nursing staff's perception regarding feasibility of using the VR equipment for each patient who had the intervention was also assessed through the questionnaire. The staff questionnaire responses will be anonymised by assigning a unique staff number for each of the staff. The list of the names of the staff and the study number allocated will be saved by the PI on a separate file.

Patient follow up will not be routinely arranged for the purpose of the study. Routine follow up as per clinical requirements will be arranged as routine for the procedure performed.

### **3.1 STUDY OUTCOME MEASURES**

Efficacy of VR in acute pain management

Feasibility of VR implementation during office gynaecology procedures

## **4. PARTICIPANT ENTRY**

### **4.1 PRE-REGISTRATION EVALUATIONS**

Clinical indications for undergoing an office hysteroscopy will be confirmed.

Staff in the outpatient hysteroscopy clinic.

### **4.2 INCLUSION CRITERIA**

**Patients:** Inclusion criteria will include all women of at least 18 – 70 years of age, planned for an office hysteroscopy.

**Staff:** Inclusion criteria will include the clinician performing the outpatient hysteroscopy and the nurse supporting the clinic.

### **4.3 EXCLUSION CRITERIA**

**Patients:**

- Hearing impairments and blindness
- Any known anatomical characteristics that may make performing the office procedure more difficult (e.g., cervical conization, Manchester Fothergill).
- The denial or withdrawal of oral informed consent

**Staff:** The denial or withdrawal of informed consent

### **4.4 WITHDRAWAL CRITERIA**

Patients and staff can withdraw from the study if they so desire at any time and without giving a reason. A decision to withdraw at any time, or a decision not to take part, will not affect the standard of care / treatment that they receive.

## **5. ADVERSE EVENTS**

## 5.1 DEFINITIONS

**Adverse Event (AE):** any untoward medical occurrence in a patient or clinical study subject.

**Serious Adverse Event (SAE):** any untoward and unexpected medical occurrence or effect that:

- **Results in death**
- **Is life-threatening** – *refers to an event in which the subject was at risk of death at the time of the event; it does not refer to an event which hypothetically might have caused death if it were more severe*
- **Requires hospitalisation, or prolongation of existing inpatients' hospitalisation**
- **Results in persistent or significant disability or incapacity**
- **Is a congenital anomaly or birth defect**

Medical judgement will be exercised in deciding whether an AE is serious in other situations. Important AEs that are not immediately life-threatening or do not result in death or hospitalisation but may jeopardise the subject or may require intervention to prevent one of the other outcomes listed in the definition above, will also be considered serious.

## 5.3 REPORTING PROCEDURES

All adverse events will be reported. Depending on the nature of the event the reporting procedures below will be followed. Any questions concerning adverse event reporting will be directed to the Chief Investigator in the first instance.

### 5.3.1 Non serious AEs

All such events, whether expected or not, will be recorded.

### 5.3.2 Serious AEs

An SAE form should be completed and faxed to the Chief Investigator within 24 hours. However, **relapse and death due to <condition>**, and hospitalisations for elective treatment of a pre-existing condition do not need reporting as SAEs.

All SAEs should be reported to **Newcastle and North Tyneside 1 National Research Ethics Committee** where in the opinion of the Chief Investigator, the event was:

- 'related', i.e. resulted from the administration of any of the research procedures; and
- 'unexpected', i.e. an event that is not listed in the protocol as an expected occurrence

Reports of related and unexpected SAEs should be submitted within 15 days of the Chief Investigator becoming aware of the event, using the NRES SAE form for non-IMP studies. The Chief Investigator must also notify the Sponsor of all SAEs.

Local investigators should report any SAEs as required by their Local Research Ethics Committee, Sponsor and/or Research & Development Office.

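### Section 5.3.2 carries an unfilled template exemption for some deaths, and sections 5.1 and 5.3.2 use the word unexpected inconsistently in SAE reporting

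*Combined protocol and SAP*

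**What the plan says.** Four places in the safety chapter of the combined protocol and SAP bear on this.

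- **Section 5.1** opens the SAE definition with "any untoward and unexpected medical occurrence or effect that" and lists five outcomes. The first is "Results in death", with no limit on cause. A paragraph after the list adds "Medical judgement will be exercised in deciding whether an AE is serious in other situations". It then extends the label to important events that fall short of the listed outcomes but may endanger the subject or that "may require intervention to prevent one of the other outcomes listed in the definition above, will also be considered serious". That paragraph does not require the event to be unexpected.
- **Section 5.3** states "All adverse events will be reported", refers the reader on to the procedures that follow according to the type of event, and adds "Any questions concerning adverse event reporting will be directed to the Chief Investigator in the first instance".
- **Section 5.3.1**, headed "Non serious AEs", has those events recorded whether or not they were expected.
- **Section 5.3.2** asks for an SAE form to the Chief Investigator within 24 hours. It exempts "relapse and death due to <condition>", and also planned admissions for an existing condition. It sends SAEs that are both related and unexpected to the ethics committee within 15 days, where unexpected means that the protocol does not list the event as expected. The Chief Investigator is to tell the Sponsor of all SAEs, and local investigators are to report any SAE as their local bodies require.

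**The concern.** There are two separate drafting faults, and neither causes the other.

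The first is the unfilled field. It is template text, not a redaction. Section 4.2 defines the patients by a planned procedure and an age range, not by a disease, so the protocol offers no condition to put there. Relapse also has no obvious meaning in a study with one procedure and no study follow-up. An exemption that mentions death therefore stands in operative text with no stated scope.

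The second is the double use of unexpected. As part of the definition, it decides whether an event is an SAE at all. As a filter in 5.3.2, it decides which SAEs go further. If every SAE is already unexpected, the filter has nothing to do; if the filter has work to do, the definition is too narrow.

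What is at stake is whether a serious event reaches the Chief Investigator and Sponsor promptly, and whether two people would classify the same event alike.

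**Working it through.** There is no figure to reproduce. The check traces each kind of event through sections 5.1, 5.3, 5.3.1 and 5.3.2.

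**Inputs counted from the text**

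- Outcomes listed in 5.1 under the unexpected condition: 5 of 5.
- Uses of that condition in the medical-judgement paragraph of 5.1: 0.
- Listed outcomes touched by the unfilled exemption: 1 (death).
- Expected occurrences listed in the supplied text: 0. The Appendices page names 7 items (questionnaires, interview questions, leaflets, consent forms). Their contents are not available, so a list there cannot be ruled out.
- Steps in 5.3.2 that depend on the SAE label alone: 3. These are the 24-hour form, the Sponsor notice (no time limit given), and local investigator reporting (as local bodies require).
- Steps that also need the event to be related and unexpected: 1, the 15-day ethics report.

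**Route of each kind of event**

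1. *Non-serious.* Recorded under 5.3.1, expected or not. No conflict.
2. *Listed serious outcome, unexpected.* An SAE under 5.1. All 3 label-only steps apply, and the ethics report too if the event is related.
3. *Listed serious outcome that staff regard as foreseeable.* The result depends on what unexpected means in 5.1:
   - *The 5.3.2 meaning, with no list.* Nothing is listed, so every event is unexpected. The event is an SAE and 0 steps are missed.
   - *The 5.3.2 meaning, with a list in an appendix.* A listed event fails the 5.1 definition, and the 3 label-only steps lapse. The ethics report is not lost, because 5.3.2 would not send a listed event to the committee anyway.
   - *The ordinary sense of the word, judged by staff.* The event fails the 5.1 definition and the 3 label-only steps lapse. If it is related and not on any list, the ethics report lapses as well: 3 + 1 = 4 steps.
4. *Lesser important event, foreseeable.* Serious under the medical-judgement paragraph, which has no such condition. Under the last two readings in item 3, a foreseeable hospitalisation could thus fall outside the definition while a lesser foreseeable event falls inside it.
5. *Death, under the unfilled exemption.* No condition is named, so no death literally meets the exemption: 0 exempt. Its intended scope cannot be determined from the text.

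**What remains for a foreseeable serious event excluded under item 3.** Section 5.3.1 is confined to non-serious events. Section 5.3 still requires it to be reported and points to the procedures that follow, but sets no deadline of its own.

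**The case against.** The strongest reply is that the gap is empty. The only definition of unexpected in the document is in 5.3.2, and the supplied text lists no expected occurrence. On that definition every event is unexpected and all steps apply. This is a fair reading and may be what the authors meant. It does not settle the matter, because 5.1 neither defines the word nor refers to 5.3.2, and a person classifying an event starts from 5.1.

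A second reply is that 5.3 sends every adverse event to one of two procedures. A foreseeable hospitalisation is plainly not non-serious, so the natural route is 5.3.2 and its 24-hour form. The first sentence of the medical-judgement paragraph could also be read to bring such an event in. Both points reduce the risk. Neither removes the conflict, since the steps in 5.3.2 attach to SAEs and 5.1 says what an SAE is.

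A third reply is that the unfilled field does no harm: with no condition named and death listed without limit, the default is to report. That holds literally. The field still invites a reader to supply a condition.

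Two stronger inferences should be resisted. A reader might conclude that the protocol exempts deaths from SAE reporting; as written it exempts none. A reader might also conclude that foreseeable serious events have no reporting route; section 5.3 gives them one, though without its own time limit.

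**Conclusion.** Both drafting faults stand, as a minor point. The exemption in 5.3.2 is unfilled and its scope undefined. The two uses of unexpected are inconsistent, and one of them is redundant or misplaced.

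The practical effect depends on the reading: 0 steps missed if 5.1 borrows the 5.3.2 meaning and no list exists; otherwise 3, or 4 for a related, unlisted event that staff judge foreseeable. This assumes that staff apply 5.1 literally, and it leaves open what the unseen appendices contain. The document gives no event rate, so the likely number of affected events cannot be stated. The study is small (40 patients, one named recruiting site, a video of at most 15 minutes). No objective, outcome measure or planned analysis changes.

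**What to change.** 1. In 5.3.2, delete the unfilled exemption, or have the sponsor and investigator replace it with a defined one that agrees with the unrestricted listing of death in 5.1.
2. Reconcile 5.1 with 5.3.2 by removing the two words that make expectedness part of the SAE definition. Expectedness, together with relatedness, then acts only as the filter for the 15-day ethics report.
3. So that the filter can be applied, list the expected occurrences in the protocol or state that there are none.

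The first two changes cost a few words in two sections; the third adds a short list or one sentence. Some extra SAE forms may follow. The statistical plan does not change.
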